6.1 Primary Objectives and Endpoints

- To assess the food effect on bioavailability ($AUC_{0-\infty}$, AUC_{0-t} and C_{max}) for Metformin 1000 mg/Gliclazide 30 mg MR, fixed dose combination, tablets, given as single dose in fasting state and with food to healthy volunteers.

6.2 Secondary Objectives and Endpoints

- To estimate pharmacokinetic parameters such as t_{max} , $t_{1/2}$, Vd and CL .
- To compare all experimental treatments' safety.

6.3

Overall Trial Design and Plan

The IMP will be given in fast and fed state. A randomized, open label, single dose, 2 x 2 cross design will be used with a 14-day washout period between 2 study stages. Treatment groups will be balanced, with the same number of subjects, who will be randomized to the dosing sequences (see table below).

Food's effect study			
Sequence	Period 1	Washout period	Period 2
1	Fast		Fed
2	Fed		Fast

All data from participant subjects should be analyzed and included in the statistical analysis, as long as they meet the established criteria.

7

Sample Size

According to the goals for the study treatment regarding postprandial/fasting, pharmacokinetic parameters will be calculated AUC and C_{max} for both analytes, Metformin and Gliclazide. In order to have an accurate and reasonable precision for the estimated ratios, a sufficient amount of subjects will be randomized.

Taking 90 % confidence interval for the postprandial/fasting ratio as a measure for accuracy and assuming an average variation coefficient of 20 % or higher for AUC (AUC $0-\infty$, AUC $0-t$) and C_{max} for Metformin y Gliclazide, then with 18 evaluable subjects the food effect on pharmacokinetics can be estimated with an accuracy of 12 % or higher. The following ratio will be carried out, being R the estimated ratio and LCL / UCL lower and higher confidence levels for the 90% confidence interval for R:

$$0.89 * R \leq LCL < UCL \leq 1,12 * R$$

An accuracy of 12% or higher will result in an accurate enough description for the food effects. Besides, 18 evaluable subjects are enough to detect a difference among treatments of 18 % or higher with a power of 80 % at least. Taking into account a drop-out rate around 20 %, 22 subjects should be randomized.

8

Overview of Planned Analyses

To determine and compare if the rate and extend of metformin and gliclazide's absorption is affected by food, metformin hydrochloride extended release (XR) 1000 mg/gliclazide 30 mg modified release (MR) in one tablet was assessed in fasting and post-prandial state, depending on the group it was assigned to. Twenty-two (22) subjects were randomized, they were randomly assigned to each of the treatment sequences and given the test formulation in two different periods (fasting and post-prandial state), with a 14-day wash-out period. According to the sampling schedule, plasma was obtained from blood samples collected and using a previously validated

analytical method, the metformin and gliclazide concentrations were determined for each subject and then they were used to determine if bioavailability of the quantified analytes is changed by food. Only twenty-one (21) subject finished the study.

This trial intends to estimate the effect of food on pharmacokinetics. It is not intended to prove or confirm statistically the lack of any food effect.

Therefore, no statistical hypothesis is presented. As primary analysis, a mixed model will be applied for all C_{\max} , AUC_{0-t} and $AUC_{0-\infty}$ for Metformin and C_{\max} , AUC_{0-t} and $AUC_{0-\infty}$ for Gliclazide, of the fixed dose combination metformin /Gliclazide log transformed. With TREATMENT, PERIOD and SEQUENCE as fixed effects, and the SUBJECT (SEQUENCE) as random effect.

Based on the residual error term 90 % confidence intervals will be built for the estimated differences postprandial - fasting, resulting in 90 % confidence intervals for postprandial/fasting ratios following the repeated transformation.

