**Study drug: dosage/route/dosing schedule:**

Fixed dose of Metformin 1000 mg/Gliclazide 30 mg MR (one tablet), single dose, given in fasting or postprandial state.

**Study duration:** Approximately seven weeks

**Statistical method:** According to the goals for the study, treatment regarding postprandial/fasting, pharmacokinetic parameters will be calculated AUC and  $C_{max}$  for both analytes, Metformin and Gliclazide. In order to have an accurate and reasonable precision for the estimated ratios, a sufficient amount of subjects will be randomized. Taking 90 % confidence interval for the postprandial/fasting ratio as a measure for accuracy and assuming an average variation coefficient of 20 % for AUC ( $AUC_{0-\infty}$ ,  $AUC_{0-t}$ ) and  $C_{max}$  for Metformin or Gliclazide, then with 18 evaluable subjects the food effect on pharmacokinetics can be estimated with an accuracy of 12 %.

The following ratio will be carried out, being R the estimated ratio and LCL/UCL lower and upper confidence limit for the 90 % confidence interval for R:

$$0.89 * R \leq LCL < UCL \leq 1,12 * R$$

An accuracy of 12 % or higher will result in an accurate description for the food effects. Besides, 18 evaluable subjects are enough to detect a difference among treatments of 18 % or higher with a power of 80 % at least. Taking into account a drop-out rate around 20 %, 22 subjects should be randomized.

This trial intends to estimate the food effects on the pharmacokinetics. It is not intended to prove or confirm statistically the lack of food effect.

Therefore, no statistical hypothesis is shown. As primary analysis, a mix model for  $C_{max}$ ,  $AUC_{0-t}$  and  $AUC_{0-\infty}$  log-transformed will be applied. With TREATMENT, PERIOD and SEQUENCE as fixed effects, and the SUBJECT (SEQUENCE) as random effect. Based on residual errors term, confidence intervals of 90 % will be built for estimated differences for postprandial - fasting, resulting in confidence intervals of 90 % for the postprandial/fasting ratios following transformation.

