### **9.1 Sample Size**

According to the goals for the study treatment regarding postprandial/fasting, pharmacokinetic parameters will be calculated AUC and  $C_{max}$  for both analytes, Metformin and Gliclazide. In order to have an accurate and reasonable precision for the estimated ratios, 22 subjects will be randomized.

Taking 90 % confidence interval for the postprandial/fasting ratio as a measure for accuracy and assuming an average variation coefficient of 20 % for AUC (AUC0-∞, AUC0-t) and Cmax for Metformin or Gliclazide, then with 18 evaluable subjects the food effect on pharmacokinetics can be estimated with an accuracy of 12 %. The following ratio will be carried out, being R the estimated ratio and LCL / UCL lower and higher confidence levels for the 90% confidence interval for R:

$$0.89 * R \leq LCL < UCL \leq 1,12 * R$$

An accuracy of 12% will result in an accurate description for the food effects. Besides, 18 evaluable subjects are enough to detect a difference among treatments of 18 % or higher with a power of 80 % at least. Taking into account a drop-out rate around 20 %, 22 subjects should be randomized.

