### Statistical Analysis

This trial intends to estimate the effect of food on pharmacokinetics. It is not intended to prove or confirm statistically the lack of any food effect.

Therefore, no statistical hypothesis is presented. As primary analysis, a mixed model will be applied for all  $C_{max}$ ,  $AUC_{0-t}$  and  $AUC_{0-\infty}$  for Metformin and  $C_{max}$ ,  $AUC_{0-t}$  and  $AUC_{0-\infty}$  for Gliclazide, of the fixed dose combination metformin /Gliclazide log transformed. With TREATMENT, PERIOD and SEQUENCE as fixed effects, and the SUBJECT (SEQUENCE) as random effect.

Based on the residual error term 90 % confidence intervals will be built for the estimated differences postprandial - fasting, resulting in 90 % confidence intervals for postprandial/fasting ratios following the repeated transformation.

Statistical comparisons between treatments A and B, with respect to  $C_{max}$ ,  $AUC_{0-t}$ , and  $AUC_{\infty}$  of Metformin/Gliclazide, will in each case separate based on a mixed linear model for log transformed (natural log) pharmacokinetic parameter data. For each parameter evaluation and each pairwise comparison, the statistical model will include covariate adjustments for period and sequence as fixed effects, and subject, nested within sequence as random effect. Carry-over effects will be assumed ignorable.

General linear model for the analysis of variance, representing the experimental design, will be used for the analysis of data for pharmacokinetic variables by considering the additive form for the following variation sources:

- ✚ Dosing sequence.
- ✚ Subjects nested in the dosing sequence called variability or residual value between subjects.
- ✚ Dosing period.
- ✚ Treatment or formulation.
- ✚ Experimental error, called variability or residual value between subjects.

That general linear model, applied to the crossed designs to determine the food effect on bioavailability is as follows:

$$Y_{ijk} = \mu + G_k + S_{jk} + P_j + F_{(j,k)} + e_{ijk} \quad (\text{Chow \& Liu, 2009})$$

Where:

$\mu$  = overall mean

$G_k$  = fixed effect of  $k^{th}$  sequence

$S_{jk}$  = randomized effect of the  $i^{th}$  subject in the  $k^{th}$  sequence, where  $i = 1, 2, \dots, n_k$  y  $k = 1, 2, \dots, K$

$P_j$  = fixed effect of the  $j^{th}$  period, where  $j = 1, 2, \dots, J$  y  $\sum_j P_j = 0$

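### SAP section 7 makes the 20 % CV an open-ended minimum but keeps 18 subjects, the 0.89R–1.12R bounds and 80 % power, which need a CV held at or near 20 %

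*SAP*

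**What the plan says.** Protocol 9.1 starts from "assuming an average variation coefficient of 20 % for AUC" and Cmax. From this it takes 18 evaluable subjects, a 90 % confidence interval for the fed/fasted ratio lying between 0.89R and 1.12R, and the statement that "18 evaluable subjects are enough to detect a difference among treatments of 18 % or higher with a power of 80 % at least". The synopsis gives the same inputs and outputs.

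SAP section 7 repeats the paragraph with one changed input: "assuming an average variation coefficient of 20 % or higher for AUC". The 18 subjects, the two bounds and the power sentence are unchanged. SAP section 5 says that the SAP rests on protocol section 9.

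The SAP also qualifies the precision: "the food effect on pharmacokinetics can be estimated with an accuracy of 12 % or higher", and again "An accuracy of 12% or higher will result in an accurate enough description for the food effects". Protocol 9.1 has no such qualifier ("An accuracy of 12% will result in an accurate description for the food effects"); the synopsis has it once ("An accuracy of 12 % or higher will result in an accurate description for the food effects").

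No document attaches a direction, scale, alpha or sidedness to the 18 % difference. The planned analysis is "a mixed linear model for log transformed (natural log) pharmacokinetic parameter data".

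**The concern.** At a fixed number of subjects, the interval widens and power falls as the CV rises. A CV with a floor and no ceiling therefore cannot support fixed bounds or a fixed minimum power. As worded, the SAP claims 12 % precision for any CV of 20 % or more, which the design does not deliver. SAP section 5 sends its content to the study report and possibly to submissions and manuscripts, so the sentence may be carried forward.

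A smaller matter is the power sentence. On a log scale an 18 % fall and an 18 % rise are effects of different size, so the sentence cannot be fully checked without its missing terms.

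**Working it through.** **Inputs.** CV 20 % (protocol 9.1 and synopsis) or higher (SAP section 7); n = 18 evaluable; 90 % interval; natural-log mixed model for a 2x2 crossover (protocol 9.5). Assumptions: the CV is within-subject, which the documents do not say but the crossover formula needs, and the 18 subjects split 9 + 9. Alpha for power is not given, so two-sided 5 % and 10 % are both shown.

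**Formulas.** σ = √ln(1 + CV²); SE = σ·√(2/n); df = n − 2; bounds = R·exp(± t(0.95, df)·SE); power from the noncentral t with noncentrality |ln ratio|/SE.

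**Reproducing the plan at CV 20 %.**
- σ = √ln(1.04) = 0.1980; SE = 0.1980·√(2/18) = 0.0660.
- t(0.95, 16) = 1.746; half-width = 1.746 × 0.0660 = 0.1153.
- exp(−0.1153) = 0.891 and exp(0.1153) = 1.122, which round to the stated 0.89 and 1.12. A normal quantile would give 0.897 and 1.115, so the bounds were evidently t-based.
- Ratio 0.82: |ln 0.82|/SE = 0.1985/0.0660 = 3.01; power 80.6 % at two-sided 5 %, 89.1 % at two-sided 10 %. The first matches the stated 80 %.

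**Raising the CV, n = 18.**

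| CV | 90 % bounds | Power at 0.82, two-sided 5 % | Power at 0.82, two-sided 10 % |
|---|---|---|---|
| 20 % | 0.891R–1.122R | 80.6 % | 89.1 % |
| 21 % | 0.886R–1.129R | 76.7 % | 86.4 % |
| 25 % | 0.867R–1.154R | 62.2 % | 74.8 % |
| 30 % | 0.843R–1.186R | 47.9 % | 61.7 % |

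**Largest CV at which each figure survives, n = 18.** Upper bound exactly 1.12: 19.7 %; lower bound exactly 0.89: 20.2 %; upper bound still rounding to 1.12: 20.4 %. Power of 80 % at ratio 0.82: 20.1 % at two-sided 5 %, 23.2 % at two-sided 10 %.

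**Subjects needed at CV 25 %.** n = 26 gives 0.890R–1.124R, which meets the bounds only after rounding. n = 28 gives 0.894R–1.119R, which meets them as written.

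**Power at a ratio of 1.18, CV 20 %, n = 18.** |ln 1.18|/SE = 0.1655/0.0660 = 2.51. Power is 65.4 % (two-sided 5 %, t), 77.5 % (two-sided 10 %, t) or 80.6 % (two-sided 10 %, normal approximation).

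**With the 21 completers reported in SAP section 8** (11 + 10 assumed): 0.900R–1.112R at CV 20 %, 0.890R–1.123R at 22 %, 0.877R–1.141R at 25 %.

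**The case against.** The best defence is that nothing depends on this. Both documents say that the trial estimates the food effect and presents no hypothesis. No decision rule uses the power. The SAP, dated March 2019, already reports 22 randomized and 21 finishers, so its section 7 could not have affected enrolment, and the achieved intervals will show the real precision. All of that stands and limits the weight of the point. It does not make the sentence true: even 21 subjects miss the bounds at CV 25 %.

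Three stronger readings may tempt a reader, and the documents do not support them.

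- **That the power statement is false for an 18 % rise.** It falls short at a ratio of 1.18 under t-based power, clearly at two-sided 5 % and by 2.5 points at two-sided 10 %. A normal approximation at two-sided 10 %, the level that matches the 90 % interval, returns 80.6 %. The t-based bounds make t the more natural guess, but the documents do not state the power method or alpha. What can be said is that terms are missing.
- **That the 80 % power also stops at CV 20 % on every reading.** For a ratio of 0.82 it lasts to about 23 % at two-sided 10 %. The limit near 20 % is firm only for the bounds.
- **That the qualifier after 12 % permits worse precision.** The displayed inequality sets outer limits, so the phrase can only mean at least that accurate. Removing it would be editorial.

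**Conclusion.** The SAP's CV assumption is wrong as written. The stated bounds belong to a CV of 20 % and fail just above it. The stated power for an 18 % decrease also fails for an open-ended CV, with a limit of about 20 % or 23 % depending on alpha. At CV 25 % the interval is 0.867R–1.154R in place of 0.89R–1.12R, and power at 0.82 is 62 % or 75 %. These figures rest on a within-subject CV, equal sequences and the planned log-scale analysis.

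The protocol's own calculation is sound at CV 20 %: the bounds reproduce, and so does the power for an 18 % decrease at two-sided 5 %. The absence of direction, scale and alpha from the power sentence is a secondary gap in reporting, not a demonstrated error. Overall impact is low.

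**What to change.** In SAP section 7, and wherever the sample-size statement is reported, restore a CV of 20 % as in protocol 9.1, or write up to 20 %. The bounds and power are then tied to the CV that produces them.

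The sponsor should also confirm which fed/fasted ratio, alpha and sidedness lie behind the 18 %, and state the power for that case. No replacement threshold should be written in before that, because the documents do not identify the alpha.

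The cost is a wording correction and one query to the sponsor.

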8.1 Interim Analysis

To assess food influence on the study drug assessed, a crossed 2-period and 2-sequence design was used, with a sampling time of 168 hours which allowed to estimate the 90% of the average AUC for the analytes.

The pharmacokinetic analysis for the plasma concentrations was performed using the WinNonlin® software with a non-compartmental model and the use of real times.

The t_{\max} and C_{\max} values were obtained from the measures taken. The area under the curve of plasma concentration from t_0 (dosing) to the t_n ($AUC_{0 \rightarrow t}$), was estimated with the trapezoidal method with lineal interpolation. To determine the area under the curve from the last sampling time to the infinite time ($AUC_{t \rightarrow \infty}$), the last plasma concentration quotient in the clearance rate was determined by lineal regression, using the sampling points from the terminal lineal logarithm which fitted the best to the straight line. The $AUC_{0 \rightarrow \infty}$ was determined adding up the $AUC_{0 \rightarrow t}$ and the $AUC_{t \rightarrow \infty}$.

The statistical analysis was performed with the WinNonlin® using the least squares with the generalized lineal model (GLM).

The intra-subject Student residual analysis for the pharmacokinetic parameters was performed with Microsoft Excel®.

The following model was used for the analysis:

$$Y_{ijkl} = \mu + S_k + V(S)_{i(k)} + P_j + F_l + e_{ijkl} \dots \dots \text{ (Chow \& Liu, 2009)}$$

Where:

Y_{ijkl}	is the response (pharmacokinetic parameter) in the i^{th} volunteer, where j is the $-^{\text{th}}$ period, and k^{th} sequence with l^{th} treatment.
μ	is the overall mean.
S_k	is the effect of the k^{th} dosing sequence.
$V(S)_{i(k)}$	is the of the i^{th} volunteer in the k^{th} sequence, which is considered a randomized effect.
P_j	is the effect of the j^{th} period (or dosing phase).
F_l	is the effect of the l^{th} treatment or formulation.
e_{ijkl}	is the experimental error, intra-volunteer variability and a randomized effect assumed with normal distribution, zero media, constant variance and independent of the volunteer's effect sequentially nested.

Based on the determination of the average square error and the determination of the geometric means, the classic 90% confidence intervals estimation was made for the test-reference ratio in the previously logarithmic transformed data. Where the test corresponds to the post-prandial conditions and the reference to fasting conditions.

9 Changes to the Planned Analyses in the Clinical Trial Protocol

The statistical methods as described in the protocol were adopted.

There are no changes to the planned analyses.

10 Protocol Deviations and Analysis Sets

10.1 Definition of Protocol Deviations and Analysis Sets

All deviations should be justified with statistical or scientific data and any change to the original statistical plan should be documented, in the study master file and in the pharmacokinetics statistical report as well as in the final study report. Subjects' data will not be replaced. Any missing data will be considered as non-existent data. Likewise, data cannot be removed from the statistical analysis, except in the following events.

- **Research Subjects with Pre-dose Concentrations in the Biological Matrix**

In the event pre-dose concentration is $< 5\%$ of the C_{max} value for a research subject, subject's data can be included without any adjustment to measurement and pharmacokinetic calculations. When pre-dose value is $> 5\%$ of the C_{max} , research subject should be removed from all study bioequivalence assessments.

- **Exclusion of data due to vomit or diarrhea.**

Data from research subjects who experience vomiting and diarrhea throughout the bioequivalence study for immediate release products can be removed from the statistical analysis if vomiting and diarrhea occur before 2 fold the median for t_{max} or 2 fold t_{max} value obtained from the research subject in a given period.

- **Research subject with very low plasma concentrations for study drugs.**

As established by NOM-177-SSA1-2013, research subjects in a cross designed who provide evaluable data for test drug and reference drug, or who do not have evaluable data in the single period of a parallel design, should not be either included in the statistical analysis.

It is considered that a research subject has very low concentrations, if the AUC is lower than 5 % of the geometric means for the reference drug's AUC (it should be calculated without including outliers). Exclusion of data due to this reason will only be accepted prior scientific rationale and review of the case by the COFEPRIS.

11

General Specifications for Statistical Analyses

Pharmacokinetic parameters (non-compartmental analysis) and statistical analysis for determining bioequivalence will be calculated using Phoenix WinNonlin 8.0 software.

The results of this trial will be reported using summary tables, figures, and data listings, as appropriate. All data will be summarized by treatment and/or scheduled time point, as appropriate.

12

Protocol Deviations

12.1

Important Protocol Deviations

Not applicable. No deviation was observed in the study

12.2

Reasons Leading to the Exclusion from an Analysis Set

- **Research Subjects with Pre-dose Concentrations in the Biological Matrix**

In the event pre-dose concentration is less than 5 % of the C_{max} value for a research subject, subject's data can be included. When pre-dose value is greater than 5 % of the C_{max} , research subjects data should be removed from all study of food effect on bioavailability.

- **Exclusion of data due to vomit or diarrhea.**

Data from research subjects who experience vomiting and diarrhea throughout the study for immediate release products can be removed from the statistical analysis if vomiting and diarrhea occur before 2 fold the median for t_{max} or 2 fold t_{max} value obtained from the research subject in a given period.

- **Research subject with very low plasma concentrations for study drugs.**

As established by NOM-177-SSA1-2013, research subjects in a cross designed who provide evaluable data for test drug and reference drug, or who do not have evaluable data in the single period of a parallel design, should not be either included in the statistical analysis.

It is considered that a research subject has very low concentrations, if the AUC is lower than 5 % of the geometric means for the reference drug's AUC (it should be calculated without including

outliers). Exclusion of data due to this reason will only be accepted prior scientific rationale and review of the case by the COFEPRIS.

13 Demographics and Other Baseline Characteristics

Demographic data from each volunteer is shown in table 13.1 and the descriptive statistics for the demographic variables from volunteers recruited in the study are shown in table 13.2. **PPD**

13.1 Demographics

Table 13.1. Demographic Variables' Individual Data

Case	Sex	Age	Weight	Height	BMI	Sequence
PPD						

Table 13.2. Demographic Variables' Descriptive Statistics

Statistics	Age (years)	Weight (kg)	Height (m)	BMI (Kg/m ²)
Mean	PPD			
SD				
Median				
25th percentil				
75th percentil				
Minimum				
Maximum				

14**Treatment Compliance and Exposure**

All subjects receive the investigational treatment at the pre-specified fixed dosage. Information relating to the extent of exposure is thus contained in the treatment labelling.

15**Endpoint Evaluation****15.1****Primary Endpoint Analyses**

The determination of pharmacokinetics parameters were determined using WinNonlin software depending of their own characteristics as follows:

C_{max}: is the peak or maximum concentration

AUC_{0-t}: area under de curve computed from time zero to the time of the last positive Y value.

AUC_{0-∞}: area under de curve computed from time zero to extrapolated from infinity.

Ke: First-order rate constant associated with the terminal (log-linear) elimination phase. This is estimated via linear regression of time vs. log concentration.

Primary pharmacokinetics parameters, AUC and C_{max}, were used to estimate the effect of food on pharmacokinetics. It is not intended to prove or confirm statistically the lack of any food effect.

As primary analysis, a mixed model will be applied for all C_{max}, AUC_{0-t} and AUC_{0-∞} for Metformin and C_{max}, AUC_{0-t} and AUC_{0-∞} for Gliclazide, of the fixed dose combination metformin /Gliclazide log transformed. With TREATMENT, PERIOD and SEQUENCE as fixed effects, and the SUBJECT (SEQUENCE) as random effect.

Based on the residual error term 90 % confidence intervals will be built for the estimated differences postprandial - fasting, resulting in 90 % confidence intervals for postprandial/fasting ratios following the repeated transformation.

Statistical comparisons between treatments A and B, with respect to C_{max} , AUC_{0-t} , and AUC_{∞} of Metformin/Gliclazide, will in each case separate based on a mixed linear model for log transformed (natural log) pharmacokinetic parameter data.

